### **WP2 - Analysis**

Aggregated, monthly cost data per patient will be modelled using two-part 'hurdle' Gamma regression models, with length of lie as a primary independent variable. Models will explore the influence of length of lie as a continuous and dichotomised variable as described in WP1. The use of monthly cost data as the primary outcome supports estimates of costs associated with length of lie for each month following the index fall event, facilitating an understanding of whether cost differences increase, decrease, or remain stable over the 12 month follow-up period.

A series of models will be developed to explore the influence of length of lie on resource use. Unadjusted models with only length of lie and month number as predictor variables will give a crude estimate of the influence of length of lie. Patient ID will be included as a random effect to account for individual level clustering.

Second, covariate-only models will establish a 'baseline' against which to assess the adjusted influence of length of lie on cost outcomes. These will include demographic data including age, sex, deprivation decile and ethnicity; clinical characteristics including comorbidities; and features of the incidence including time of year, time of day and distance to nearest ED. The precise list of covariates will depend on data quality and learning from WP1.

Finally, fully adjusted models will include length of lie as a main predictor in conjunction with covariates listed above. This will give adjusted estimates of the effect of length of lie. Likelihood ratio tests will compare the adjusted models with the baseline models to determine the impact of including length of lie as a predictor over and above the covariates. The above models will be developed for all healthcare related costs, and separately for costs related to ED attendances, acute admissions, ambulance calls, NHS 111 calls and outpatient costs.

The primary analysis will consider 'Month 1' to be the calendar month in which the index fall occurs. This will therefore consider month 1 to be the same for falls occurring on the first or last day of the month. This may result in issues around the accuracy of predictions of monthly costs (although distribution is expected to be the same for long and short length of lie). Sensitivity analysis will examine a different date alignment, whereby 'Month 1' will be considered the same calendar month for a fall occurring in the first half of a month, and the subsequent calendar month for a fall occurring in the second half of a month.

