The resulting dataset will be used to quantify patients' care trajectory and resource use. Outcomes will include: mortality, ambulance service use, ED resource use (tests, re-attendance), hospital resource use (initial length of stay, reattendance), outpatient use (e.g. tissue viability services), discharge location (including escalation of care needs) and any subsequent ambulance re-contact or hospital reattendance. Data on service factors such as ED wait and hospital occupancy will be collected as these may impact on care. This data will enable an understanding of any differences in care trajectories between patients who have had a long lie, and those whose fall did not result in a long lie.

The relationship between length of lie and key outcome variables will be explored using descriptive and visualisation methods. The impact of the length of lie on key outcomes via a series of regression models will be explored (logistic,

Poisson and other), using different definitions of long lie (including the 1 hour NICE definition) and adjusting for appropriate demographic covariates. This will quantify the impact of a long lie on patient health outcomes, and indicate whether 1 hour is the most appropriate threshold to consider a long lie in terms of health outcomes. The analysis will explore the impact of environmental, geographical and seasonal variables on the length of lie to provide an indication of the factors driving the likelihood of a long lie and enable understanding of targets for future interventions that may influence key outcomes.

Due to the period of analysis including the Covid-19 pandemic, analyses will account for Covid-19 in two ways. Firstly, a categorical covariate will indicate whether a covid lockdown was in place nationally at the time of the long lie. Secondly, a continuous variable consisting of the number of Covid hospital beds will indicate the severity of the pandemic at the time of the long lie. Although it is acknowledged that the impacts of covid are likely to be highly complex, this should not differentially affect those who do and do not have a long lie at a given date (although may affect the balance of those groups). To explore this a sensitivity analysis will be performed including the month of the long lie as a covariate. This will allow us to gain an understanding of any change in the effect of a long lie over time, which will indicate any differences associated with covid lockdowns or pandemic severity.

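### The WP1 Covid check cannot show change in the long-lie effect over time, and the WP2 monthly cost models as listed contain no term that estimates it

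*Protocol*

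**What the plan says.** **WP1 (Protocol section 5, WP1 - Data collection).** Covid enters the outcome models through two covariates: national lockdown status and number of Covid beds. The protocol expects that Covid will not affect patients with and without a long lie differently at a given date. To examine this, "a sensitivity analysis will be performed including the month of the long lie as a covariate". The next sentence claims "This will allow us to gain an understanding of any change in the effect of a long lie over time", and says this will reveal differences linked to lockdowns or pandemic severity.

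**WP2 (Protocol section 5, WP2 - Analysis).** "Aggregated, monthly cost data per patient will be modelled using two-part 'hurdle' Gamma regression models". The stated gain from monthly data is "facilitating an understanding of whether cost differences increase, decrease, or remain stable over the 12 month follow-up period". The models then described are:

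- unadjusted: "Unadjusted models with only length of lie and month number as predictor variables", with patient as a random effect;
- baseline: covariates only, covering demographics, comorbidities and "features of the incidence including time of year, time of day and distance to nearest ED";
- adjusted: "fully adjusted models will include length of lie as a main predictor in conjunction with covariates listed above".

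For inference, "Likelihood ratio tests will compare the adjusted models with the baseline models", to judge what length of lie adds. The protocol nowhere mentions an interaction, a stratified fit or a separate model for each month.

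**The concern.** Whether an effect changes over time is a question of effect modification. It needs a term that lets the long-lie coefficient differ between periods, or separate fits by period. A time variable entered as a covariate answers another question: whether the outcome level differs between periods.

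In WP1 the protocol names such a covariate and says it will deliver the effect-change result. The analysis would return one long-lie estimate, and the expectation that Covid does not act differentially would remain untested. In WP2 the time course of the cost difference is the stated reason for modelling monthly costs. If the listed terms are used as they stand, the reported course comes from the model's form and the baseline cost curve, not from data on long lies. Twelve-month resource use is a study objective and feeds the WP7 recommendations.

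**Working it through.** The protocol gives no figure to reproduce; the point concerns model structure. From WP1 - Data collection come at least 115,000 cases, about 16,000 long lies (16,000/115,000 = 13.9%) and 24 months of index cases. All effect sizes, costs and link functions below are assumptions.

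**1. WP1.** With L = 1 for a long lie and t the calendar month, the model as written is

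logit P(Y=1) = α_t + βL.

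The effect in every month is β. Simulated data: 115,000 cases, 13.9% long lies, log odds ratio 0.6 in months 1 to 12 (odds ratio e^0.6 = 1.82) and 0 in months 13 to 24 (1.00).

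| Model | Long-lie odds ratio |
|---|---|
| lie only | 1.33 |
| lie + month | 1.33 |
| lie × period, with month | 1.75 early, 1.00 late |

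The single estimate lies near the midpoint on the log scale (e^0.3 = 1.35). In real data, adding month could move it if long lies cluster in certain months. That movement would reflect adjustment for calendar time, not change in the effect.

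**2. WP2, structure.** With logit and log links and follow-up month m:

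logit P(C>0) = α_m + βL; log E(C | C>0) = γ_m + δL.

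The odds ratio e^β and the cost ratio among patients with any cost, e^δ, do not depend on m. A patient random intercept does not alter this. The difference in expected cost is

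D_m = e^(γ_m) × [p_m(1)·e^δ − p_m(0)],

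where p_m(L) is the probability of any cost in month m. It varies with m only through baseline use and baseline cost.

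**3. WP2, simulation.** 20,000 patients × 12 months, 13.9% long lies. Baseline logit is −0.5 − 0.12(m−1); baseline mean cost among users is 1,500·exp(−0.05(m−1)). Month is a factor and the random effect is omitted. In the growing scenario the log odds ratio is 0.8(m−1)/11 and the log cost ratio 0.4(m−1)/11. Check of the true value at month 12:

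- no long lie: 0.139 × 865 = 121;
- long lie: 0.265 × 1,291 = 342;
- difference: 221.

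Long-lie cost difference in pounds at months 1 / 6 / 12:

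| Scenario | True | lie + month | lie × month |
|---|---|---|---|
| growing | 0 / 162 / 221 | 262 / 158 / 84 | 0 / 173 / 220 |
| fading | 719 / 202 / 0 | 393 / 225 / 90 | 726 / 176 / 0 |
| crossing | 221 / 12 / −50 | 26 / 16 / 8 | 228 / 28 / −43 |
| constant ratios | 304 / 182 / 85 | 306 / 188 / 88 | 299 / 163 / 84 |

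The lie + month column falls in all four scenarios because baseline cost falls. In the growing scenario its coefficients are 0.349 (log odds ratio) and 0.191 (log cost ratio) in all 12 months. The likelihood ratio statistic for the interaction in the logistic part, on 11 degrees of freedom, is 410, 395, 619 and 12.7 in the order of the table. The last is close to the 11 expected when there is no interaction.

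**4. A hand-checkable case, gamma part only, equal groups.** Take true cost ratios R_m of 1.5, 1.25 and 1.1 in months 1 to 3, then 1.0, and comparator costs c_m of 3,000, 900 and 600, then 400. The fitted common ratio r solves Σ (R_m/r)/(1 + R_m/r) = 6. At r = 1.062 the sum is 0.586 + 0.541 + 0.509 + 9 × 0.485 = 6.00. The fitted comparator mean is c_m(1 + R_m/r)/2:

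- month 1: 3,000 × 2.412/2 = 3,619, excess 0.062 × 3,619 = 224 (true 1,500);
- month 12: 400 × 1.942/2 = 388, excess 0.062 × 388 = 24 (true 0).

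With 13.9% long lies in place of equal groups, the ratio is 1.068 and the excesses are 216 and 27.

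**5. Adjusted model and test.** The listed covariates contain time of year and time of day but not follow-up month. The planned likelihood ratio test compares models with and without length of lie, so it addresses the overall association, not its course over months.

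**The case against.** The best defence concerns WP2. The sentence about lie and month number describes the unadjusted model, whose declared purpose is a crude estimate. It lists variables, not model terms. The protocol also says monthly data will support estimates for each month, which suggests that month-specific effects are intended. Nothing excludes an interaction, and a full SAP, not shown here, could supply one. This stands as far as it goes: WP2 is a mismatch between aim and listed models, not proof that the final analysis will be wrong. The explicit room for later change, however, concerns the choice of covariates. The defence does not reach WP1, which names the term and states what it will show.

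Three stronger readings are tempting and are not supported:

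- **That WP2 would report stable cost differences by construction.** With month in the model, only the odds ratio and cost ratio are fixed, and only under links that the protocol does not state. Differences in pounds vary, as the 224 and 24 above show. An adjusted model with no month term at all would give no time course, but that covariate list is open-ended.
- **That calling length of lie a main predictor means main effects only.** In context it means the principal predictor added to the baseline model.
- **That the overall results are invalid.** The average long-lie association and the planned likelihood ratio test still address what they are built for. The Covid check is a sensitivity analysis beside a primary analysis described as associative.

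It is also fair to say that every effect and cost in the illustrations is assumed.

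**Conclusion.** The point holds in two strengths. In WP1 the protocol is wrong as written: month as a covariate cannot show change in the long-lie effect, whatever the data. In the illustration, an effect that disappears halfway through leaves no trace (1.33 with and without month). In WP2 the aim of tracing cost differences over 12 months is not met by the models listed. They name no lie-by-month term, the adjusted covariates omit follow-up month, and the test is of the overall lie effect. Under assumed logit and log links the ratios are held constant, and the profile in pounds is inherited from baseline cost, to the extent that it can run opposite to the truth. The size of the distortion depends on assumed costs, ratios and group shares; its existence follows from the model form. An SAP could close the WP2 gap without contradicting the protocol. The WP1 claim itself needs correcting.

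**What to change.** **WP1 sensitivity analysis.** Add long lie × calendar period (month-year or broader pandemic periods), and long lie × lockdown status or × Covid beds. Test these terms and report period-specific long-lie estimates. If month is kept only as a covariate, withdraw the claim that it shows change in effect.

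**WP2.** State the link functions. Put follow-up month in the baseline and adjusted models. Add length of lie × month (factor or spline) to both hurdle parts. Test the interaction separately from the overall lie effect, and report month-specific marginal cost differences with intervals.

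**Cost.** No new data are needed. The change adds a few model terms (11 per hurdle part for a two-level lie variable with month as a factor, fewer with a spline) and somewhat widens the month-specific intervals. These would be widest late in follow-up, where the protocol already expects censoring at a further fall to reduce precision. With about 115,000 cases this should be affordable. Any numerical illustration carried into the SAP should be labelled as resting on assumed costs, ratios and group shares.

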## **WP2 Understand the resource use of ambulance service patients after their fall**

### **WP2 - Data collection**

Urgent and Emergency Care service access events in the 12 months following an ambulance call after a fall will be assigned a unit cost based on Healthcare Resource Group (HRG) reference costs. These events include ambulance journeys, ED attendances, acute, non-elective inpatient admissions and subsequent hospital stays and outpatient events (where available). Where possible, this will be calculated using the NHS National Schedule of Costs (NHS England 2021/22 cost data) for the appropriate year. In the event that HRG codes are unavailable in CUREd+, estimated costs will be calculated based on average costs by specialty, attendance type, or ambulance service level. Where costs for that year may not be available, costs for the most recent available year will be used and adjusted using the NHS Cost Inflation Index (Jones 2023). Costs will be aggregated on a monthly basis to produce a total cost per patient per month for the 12 months following a fall.

In the event additional fall events occur within the 12-month fall follow-up period for a given patient, the additional fall will be considered a new 'index' event. The initial 12-month follow-up period related to the first fall will be censored and costs subsequent to the second fall will be modelled as occurring in the new 12-month follow-up. This will be adjusted for in the regression models. This is likely to result in wider confidence intervals for later months in the follow-up period. Confidence intervals will also be impacted for the loss of patients to follow-up, through either missing data, migration, or death during the follow-up period.

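### WP2 names a random effect for patient but none for the index fall, so inference on length of lie is too liberal to the extent that repeat fallers' costs differ between falls

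*Protocol*

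**What the plan says.** Under WP2 - Data collection, the outcome is monthly: "Costs will be aggregated on a monthly basis to produce a total cost per patient per month for the 12 months following a fall". If a patient falls again within the 12 months, "the additional fall will be considered a new 'index' event". The first series is censored at that point, and "costs subsequent to the second fall will be modelled as occurring in the new 12-month follow-up". Of this arrangement the section says "This will be adjusted for in the regression models", with no method.

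Under WP2 - Analysis, monthly costs are "modelled using two-part 'hurdle' Gamma regression models, with length of lie as a primary independent variable". The only clustering term is given in the paragraph on the unadjusted models: "Patient ID will be included as a random effect to account for individual level clustering". A covariate-only baseline follows, and then "fully adjusted models will include length of lie as a main predictor in conjunction with covariates listed above". The test of length of lie is the comparison of these two: "Likelihood ratio tests will compare the adjusted models with the baseline models". No index-fall term, robust variance or within-episode correlation is named.

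**The concern.** Length of lie is fixed within a fall and can differ between falls of one patient. A patient-only random effect assumes that, given the patient, two months of the same fall episode are no more alike than two months from different episodes. A fall that causes a fracture and a long admission breaks that assumption, because it raises several months of its own episode and not those of the patient's other episode. For a patient with one short-lie and one long-lie fall, the model then reads up to 24 monthly values as independent evidence on lie length, although only two falls were observed.

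At stake is the comparison that decides whether length of lie adds cost beyond the covariates. It is planned for total cost and again for five cost categories. If the months are over-counted, intervals are too narrow, and chance differences between falls can be read as a cost of the lie.

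**Working it through.** **No figure to reproduce.** The protocol gives no alpha, power or sample size for the WP2 test. The check is therefore of the test's type I error under the named structure, assuming a nominal 5% level and a chi-square test on 1 degree of freedom.

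**Inputs from the protocol.**
- Months within falls within patients, up to 12 months per fall, with the earlier series censored at the next fall (WP2 - Data collection).
- Patient as the only random effect, with a likelihood ratio test of length of lie (WP2 - Analysis).
- 35% long lies among patients found on the floor (section 1.1).
- About 10% of falls cause a fracture (section 1.3), and fall severity is recognised as a possible confounder (WP1 - Analyses). The WP2 covariate list has no injury or severity item. Fall-level variance above zero is therefore plausible, but its size is not given.

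**Assumed inputs.** Repeat fallers 0% to 50% of patients, with two or three falls each. Patient variance 20% of the total. Fall-level variance 0%, 5%, 10% or 20%. Correlation of lie status between falls of one patient 0.1 or 0.4. The protocol counts cases and gives neither the number of distinct patients nor the repeat-fall share.

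**Mechanism by hand.** Take a patient with two falls, each followed for 12 months. Let v_f be the fall-level variance and v_e the residual monthly variance, so that v_e = 1 − 0.20 − v_f.
- True variance of the difference between the two episode means: 2(v_f + v_e/12).
- Variance if months are independent given the patient: 2v_e/12.
- Ratio: 1 + 12·v_f/v_e.

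| v_f | v_e | Ratio | Standard error too small by a factor of |
|---|---|---|---|
| 0 | 0.80 | 1 | 1 |
| 0.05 | 0.75 | 1 + 0.60/0.75 = 1.8 | √1.8 = 1.34 |
| 0.10 | 0.70 | 1 + 1.20/0.70 = 2.71 | √2.71 = 1.65 |
| 0.20 | 0.60 | 1 + 2.40/0.60 = 5.0 | √5.0 = 2.24 |

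This applies to the within-patient contrast only. It overstates the effect on the whole analysis: censoring shortens the first series, the fitted residual variance absorbs part of v_f, and single fallers contribute correctly weighted information.

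**Simulation, Gaussian stand-in for the log-cost part.** 2,000 patients, no true effect of lie length, 1,000 runs per setting, Monte Carlo standard error √(0.05 × 0.95/1000) = 0.7 points.

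| Setting | Type I error, patient effect only |
|---|---|
| No repeat fallers (v_f 10%) | 4.4% and 6.2% |
| v_f 0%, 10% to 50% repeat fallers | 4.3% to 5.8% |
| v_f 5%, same range | 5.6% to 10.3% |
| v_f 10%, same range | 8.3% to 15.2% |
| v_f 20%, same range | 15.7% to 25.2% |

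**Simulation, logistic model for the hurdle part.** 1,500 patients, 400 runs per setting, Monte Carlo standard error √(0.05 × 0.95/400) = 1.1 points, patient variance 1 on the logit scale.
- No repeat fallers: 4.8%.
- 20% or 40% repeat fallers, no fall variance: 2.8% and 3.5%.
- 20% repeat fallers, fall variance 0.3 and 0.8: 8.3% and 11.8%.
- 40% repeat fallers, fall variance 0.3 and 0.8: 8.5% and 15.8%.

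**With fall within patient added.** In the Gaussian settings with 20% or 50% repeat fallers and v_f 10% or 20%, type I error is 4.8% to 6.7%, against 10.8% to 25.2% for the patient-only model in the same settings. Inflation is absent when either repeat fallers or fall-level variance is absent, and it goes when the fall term is added. That identifies the missing term as the cause.

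**The case against.** The best defence is that the protocol sees the repeat-fall problem and announces an adjustment, so the method is left to an analysis plan that may exist. This stands in part: the adjustment sentence shows intent and could be made to cover the point. But the protocol does fix a clustering term, and it is at patient level. The most natural adjustment, a covariate for prior fall or fall order, shifts the mean and leaves the months of one fall correlated.

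A second defence is that the harm is conditional, and this stands in full. Single fallers are unaffected, because the patient effect absorbs their fall effect. The covariate list is open and already includes comorbidities and features of the incident. The clinical-risk covariate planned for WP1 could be carried over and would absorb part of the fall-level variance. The simulations have no covariates and do not fit the full hurdle Gamma model, and their upper figures need a fall-level variance that the documents do not supply.

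A third is that the aim is to understand resource use, no alpha is set, and the cohort is large (at least 115,000 cases). Size does not cure a wrong variance structure. It is true, though, that nothing here shows any particular cost conclusion would change.

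A reader might also infer that the covariate-only and adjusted models have no random effect and no month term, because both are mentioned only with the unadjusted models, so that the test would treat all monthly costs as independent. The text does not support this. The stated reason, clustering within individuals, applies to the whole series of models, and the declared aim of estimating costs for each month after the fall needs month in them. It is a wording gap only.

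**Conclusion.** The point holds in conditional form. The protocol creates a three-level structure, puts the exposure at the middle level, and names a random effect only at the top level. For repeat fallers this over-counts months whenever costs vary between falls of the same patient beyond the covariates. The protocol's own fracture figure and the lack of a severity covariate in WP2 make that plausible.

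Under the assumptions above, true error at nominal 5% ranges from nominal (no fall-level variance or no repeat fallers), through about 6% to 10% (fall-level variance 5% of the total) and 8% to 15% (10%), to 16% to 25% (20%). Since the repeat-fall share and the fall-level variance are not in the documents, none of these can be called the expected figure. A flat statement that the WP2 p-values and intervals are wrong would go too far.

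**What to change.** In both parts of the hurdle model, specify random intercepts for index fall nested within patient. If this does not converge, use patient-clustered robust variance with a Wald test in place of the likelihood ratio test. Say that this is how the announced adjustment for repeat falls deals with clustering.

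As a clarification of wording, state that the covariate-only and fully adjusted models carry the same random effects and month number, so that the two differ only in length of lie.

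The cost is a line or two of text, a longer and harder fit, and slightly wider intervals. No new data are needed, because the new-index rule already implies an identifier for each index fall.

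### WP2 counts costs by calendar month, so Month 1 holds 1 to 31 post-fall days, and the sensitivity analysis starts Month 1 after the fall for about half the patients without saying where their index costs go

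*Protocol*

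**What the plan says.** The protocol's section on WP2 data collection defines the costing window from the call: "Urgent and Emergency Care service access events in the 12 months following an ambulance call after a fall will be assigned a unit cost". It then defines the outcome: "Costs will be aggregated on a monthly basis to produce a total cost per patient per month for the 12 months following a fall". The costed events are listed there too: "These events include ambulance journeys, ED attendances, acute, non-elective inpatient admissions and subsequent hospital stays and outpatient events (where available".

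The WP2 analysis section sets a different clock: "The primary analysis will consider 'Month 1' to be the calendar month in which the index fall occurs". It spells out the consequence: "This will therefore consider month 1 to be the same for falls occurring on the first or last day of the month". It also discloses a limitation, which it expects to affect both lie groups alike: "This may result in issues around the accuracy of predictions of monthly costs (although distribution is expected to be the same for long and short".

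The planned sensitivity analysis keeps the calendar month of the fall as Month 1 for first-half falls. Otherwise Month 1 becomes "the subsequent calendar month for a fall occurring in the second half of a month".

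The same section gives the reason for modelling monthly costs: to estimate the cost associated with length of lie in each month after the index fall, and so to see whether the difference grows, shrinks or holds steady over the year. The crude model contains only length of lie and month number as predictors, plus a patient random effect.

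**The concern.** Month number is meant to measure time since the fall. Under the primary rule it measures time since the start of a calendar month, and the two differ by up to 30 days. The early months should show the index episode and its immediate aftermath, and these are the months where the mismatch matters most.

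The sensitivity analysis is meant to show whether this matters. For falls in the second half of a month it starts the clock after the index event, and no earlier period is defined to hold the index costs. At stake are the level and shape of the monthly cost curve and the ability of the sensitivity analysis to test it.

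**Working it through.** The protocol gives no figure for days per month, so there is nothing of its own to reproduce.

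**Assumptions.** One index fall was placed on every day of a 24-month window (the protocol's accrual length). Windows starting 1 April 2019 and 1 April 2020 were both tried. Falls are taken as uniform over days. Second half means after day 15; using more than half the month's length changes the results only slightly.

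**Primary alignment.** For a fall on day *d* of a month with *L* days:
- Post-fall days in Month 1 = *L* − *d* + 1. The range is 1 to 31 and the mean 15.7; 23% of falls have 7 days or fewer.
- Days in Months 1 to 12 = 365 − (*d* − 1), or one more when the span includes 29 February. Day 31 gives 335 and day 1 gives 365 or 366. The mean is 350.3 to 350.7.
- A cost that accrues evenly over time is therefore captured in Month 1 at about 15.7 / 30.4 = 52% of a full month's amount.

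**Sensitivity alignment.**
- Share of falls in the second half: 51%.
- For these, Month 1 begins *L* − *d* + 1 days after the fall, counting the day of the fall: range 1 to 16, mean about 8.2.
- Their Month 12 ends 366 to 382 days after the fall (365 or 366, plus 1 to 16), which runs past the 12 months that are costed.
- If costs before Month 1 are dropped, the index-day ambulance and ED costs of about half the cohort are lost.
- If they are folded into Month 1, it holds 14 to 31 days for first-half falls and 29 to 47 days for second-half falls. The 12 months together then cover 351 to 382 days.

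**Can equal fall dates in both groups still distort the profile?** This is an illustration only, with assumed inputs and per-day costing: half the patients admitted, 350 GBP per day, exponential stays with mean 8 days (short lie) or 12 days (long lie), and identical fall dates. The expected difference between days *a* and *b* is 0.5 × 350 × [12(e^(−a/12) − e^(−b/12)) − 8(e^(−a/8) − e^(−b/8))].
- Months counted from the fall (365/12 = 30.4 days). Month 1: 175 × (11.05 − 7.82) = about 565 GBP. Month 2: 175 × (0.876 − 0.175) = about 123 GBP. The difference falls.
- Calendar months, averaged over the fall dates above. Month 1: about 307 GBP. Month 2: about 343 GBP. The difference appears to rise.

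The amounts depend on these assumptions. If each admission is one event dated at admission, nearly all index cost stays in Month 1 and this reversal does not arise.

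**The case against.** The strongest defence has three parts.

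First, the primary limitation is disclosed, and day of the month has no evident link to length of lie. That stands: nothing here shows bias in the overall long-versus-short contrast, although a reader might infer it. The defence does not extend to the time profile, because equal blurring in both groups still moves early differences into a later month.

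Second, a reader might infer that the sensitivity analysis deletes the index costs of second-half falls. The protocol does not say so. Its costing window starts at the ambulance call, so folding those costs into Month 1 is an equally possible reading, and a stay dated at discharge could fall in Month 1 anyway. This also stands: the supportable statement is that the place of these costs is undefined.

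Third, the protocol assigns a unit cost to each event from HRG reference costs and mentions no per-day costing. Dating admissions at admission would keep most index cost in the primary Month 1. This stands as well, so no GBP figure should be read as an estimate of the distortion. It does not help the unequal exposure in Month 1, the uneven total window or later contacts, and it puts the index admission of second-half falls before the sensitivity Month 1.

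**Conclusion.** The concern holds as a should-fix point. The calendar rule is stated in the protocol and does not match the protocol's own 12-month window from the call. Month 1 contains 1 to 31 post-fall days and the year 335 to 366. How far this blurs the early months depends on how stays are costed and dated, which the protocol does not fix.

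The sensitivity analysis does not resolve the problem. For about 51% of patients Month 1 starts 1 to 16 days after the fall, and under either treatment of the earlier costs one misalignment replaces another. The day counts follow from the calendar; the means and shares also assume evenly spread fall dates.

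**What to change.** Define Months 1 to 12 as consecutive twelfths of 365 days from the index call timestamp for every patient, with the index event in Month 1. Blocks of 30 days are less suitable, since 12 × 30 = 360 days falls short of the year. Keep time of year of the index call, already a listed covariate, to carry season. State whether an inpatient cost is dated at admission, at discharge or spread over the stay.

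Drop both calendar alignments, or keep the present primary alignment only as a sensitivity analysis. If the shifted alignment is retained, say where costs between the fall and Month 1 are counted, and reconcile it with the 12-month costing window.

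The cost is a line of data derivation and a short text edit. No new data are needed: the time-to-first-event outcomes in WP1.2 already require dated events.
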